### 1.1 Primary Objective

The primary objective is to assess pelvic floor muscle contraction with SES

**Key Endpoints:** *Displacement of bladder base during contraction.*

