## **2.2 Study Rationale**

Use of intravaginal EMS for treatment of SUI is predicated on the assumption that proximity of the electrodes to the pelvic floor muscles is of primary importance. This is largely accurate. However, appreciating that subjects who seek help most often ultimately fail treatment due to adoption and compliance issues, it is equally important to consider whether the psychological or physiological barriers associated with intravaginal EMS offset any benefit from the treatment's intimate electrode placement.

Several recent clinical reports suggest that a pattern of surface electrodes placed in the suprapubic and ischial tuberosity regions are as effective as intravaginal electrodes at retraining the pelvic floor muscles. In these studies, treatment was administered by a clinician who placed four separate electrodes on the defined tissue region and delivered prescribed pulse waves during regular training sessions. Unfortunately, the need to deliver this treatment in a clinical environment makes it burdensome to the subject and the health system.

Building on these findings, Elidah has developed a wearable, SUI specific EMS device configured for application by the subject and for use outside the clinic, allowing treatment at home and potentially accelerating the rate and efficacy of muscle retraining. This surface EMS device (SES) has been used clinically, with subject's confirmation of pelvic floor contractions. However, a more objective proof that the pelvic floor is actually contracting was requested, and subsequently an identification of which pelvic floor muscles would allow insight into the mechanism of SES.

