### 3.9 Randomization/ Blinding

Not Applicable - as this is a single-arm acute study with no randomization.

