### 4.4 Ultrasound

Subjects will place the electrode on their perineal area based on instructions, and a test should be completed to see if the subject feels a contraction while slowly incrementing the generator. If the subject is not getting good skin contact, hair may need to be trimmed or shaved. If the subject feels there is not much of a contraction, the electrode can be repositioned (usually one inch posteriorly).

Subjects should be placed in a comfortable supine position with hips and knees flexed to 60°, with lumbar spine positioned in neutral position. (Subjects may have underwear/clothes on over electrode.) Subjects should not see the US image.

With transabdominal ultrasound imaging (ex. GE Voluson E6 ultrasound with a 5-9D curved linear array GE RIC probe), the probe should be placed supra-pubically, on the lower abdomen, in the mid-sagittal plane. The transducer should be angled to obtain a clear image of the inferior-posterior aspect of the bladder. A marker should be placed at the bladder base on the junction of the hyper- and hypo-echoic areas in the region at rest. A marker should be placed, marking the maximal displacement of the bladder base from resting position:

- 1) while doing a PFM Kegel contraction (Instructions should be the same to all: to draw in and lift the PFM.)
- 2) with the generator on, slowly incrementing, counting the clicks and making note of when they first feel a contraction, until a maximum comfortable intensity level.
- 3) at the maximum comfortable intensity level *while* doing a PFM Kegel contraction combined.

4) (Optional) with a second generator (Waveform B) on at maximum comfortable intensity level

After the three images and max displacement recorded, the test should be repeated and potentially the intensity increased to a new maximum level (the skin may get numb after which intensity increased.) There should be a minimum of 7 ultrasound images (1 baseline, 2 with Kegels, 2 with generator, 2 with Kegels and generator.)

Any evidence of prolapse visualized using ultrasound should be recorded on Case Report Form.

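### The displacement markers appear to be placed in session by someone who knows the condition; a single-arm design does not prevent masked reading, and partial masking is cheap

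*Combined protocol and SAP*

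**What the plan says.** Section 1.1 names the key endpoint as "Displacement of bladder base during contraction", and Section 8.4.1 gives the primary outcome as pelvic floor movement under stimulation. Section 2.2 explains why an imaging measure is wanted: subjects had already reported contractions, and "a more objective proof that the pelvic floor is actually contracting was requested".

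Section 4.4 sets out the measurement. One marker goes on the bladder base at rest. Then, for each numbered condition (Kegel, generator, both together, and optionally a second waveform): "A marker should be placed, marking the maximal displacement of the bladder base from resting position". The generator step is done "with the generator on, slowly incrementing, counting the clicks and making note of when they first feel a contraction". On timing: "After the three images and max displacement recorded, the test should be repeated". On quantity: "There should be a minimum of 7 ultrasound images (1 baseline, 2 with Kegels, 2 with generator, 2 with Kegels and generator".

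The only masking in the plan concerns the woman: "Subjects should not see the US image". The whole of Section 3.9, which covers both randomization and blinding, reads "Not Applicable - as this is a single-arm acute study with no randomization". Sections 9.2 and 9.4.3 defer the statistical analysis plan to a later document. Nothing in the present text asks for coded, shuffled, masked or repeat reading.

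**The concern.** Finding the bladder base at an echo boundary and deciding which moment is maximal are both judgements. If the person making them knows that the stimulator is on and expects movement, a small lean in marker placement passes straight into the primary result. There is no sham condition, masked reading or reliability check that would show it.

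The reason given in 3.9 does not answer this. Having one arm means there is no allocation to conceal. It does not stop images from different conditions in the same woman being coded and read without knowledge of the condition. Both outcomes are within-woman contrasts: stimulation against rest for the primary (8.4.1), and stimulation, Kegel and both against one another for the secondary (8.4.2). What is at stake is how much weight the measurement can bear as evidence more objective than the woman's own report.

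**Working it through.** **Who knows what, and when.** Three statements in 4.4 bear on this.
1. Conditions are numbered steps with no random order.
2. The generator is stepped up while clicks are counted, so the condition is evident in the room.
3. Maximal displacement is recorded before the repeat run, so it is read in session.

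Together these imply a reader who knows the condition. This is an inference, because the text does not name who places the markers.

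**The plan's own figures.**
- Completers (8.2): 8 enrolled × (1 − 0.20) = 6.4, in line with the 5-6 in the table.
- Images per woman (4.4): 1 + 2 + 2 + 2 = 7, as stated.
- Minimum images in total: 7 × 8 = 56 at the target, 7 × 12 = 84 at the maximum in 3.3.
- There is no power calculation, test, alpha, SD or measurement error to reproduce.

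**Illustration of what a reading bias would do.** All of these inputs are assumptions:
- true displacement is zero;
- the reader adds a constant bias b, in units of the between-woman SD of the measured difference from rest;
- the test is a two-sided 5% paired t-test.

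The test statistic then follows a noncentral t distribution with n − 1 degrees of freedom and noncentrality b√n. The false-positive rate is P(|T| > t critical).

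| n | b√n at b = 0.25 | rate | b√n at b = 0.5 | rate |
|---|---|---|---|---|
| 5 | 0.56 | 7.2% | 1.12 | 14.1% |
| 6 | 0.61 | 8.0% | 1.22 | 17.1% |
| 8 | 0.71 | 9.4% | 1.41 | 23.2% |
| 12 | 0.87 | 12.4% | 1.73 | 35.3% |

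The rows for 5 and 6 match the projected completers, 8 is the target and 12 the maximum. For a fixed bias the rate rises with n, so recruiting more women does not help.

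**Choosing the maximum.** This is a separate effect. If the largest of k independent pure-noise readings is kept, its expected value is 0.56, 1.16 or 1.54 noise SDs above zero for k = 2, 5 or 10 (by simulation). Masked marker placement on a still that has already been chosen does not remove this.

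**The case against.** The strongest reply is that the masking on offer is incomplete and the plan is modest. Much of this stands.

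- **Image availability.** Section 4.4 requires at least 7 images but does not say that they are kept, or kept without markers on them. A reader might infer that clean stored images are already available for re-reading; the documents do not say so. The fix has to ask for them.
- **The rest reference.** Only one baseline image is required, and displacement is measured from rest. The end of 4.4 allows the probe to be moved while the generator is on. One rest image may not share a frame of reference with six later images.
- **What masking cannot reach.** Choosing the maximal frame and holding the probe are done live. With 5-12 women the operator may also remember images. A reader might infer that coded re-reading makes the endpoint fully masked. It would mask marker placement only, and 3.9 should not claim more.
- **Who codes.** The auditor in 9.2 is meant to have no direct contact with study data and data move to the sponsor at close-out, so that person is an awkward choice.
- **Size of bias.** The values 0.25 and 0.5 SD have no source in the documents. A reader might infer from the table that the trial's result will be false at those rates. The documents show exposure to bias, not its presence, direction or amount.
- **The claim itself.** Section 2.2 says more objective, relative to self-report. Imaging can meet that comparison without a masked reader.
- **Deferred plan.** A later analysis plan could set a reading rule. It could not recover unmarked frames that were never saved, so the matter belongs in 4.4.

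None of this makes the single-arm design a reason to leave the reader unmasked.

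**Conclusion.** The point holds as a limited one. As written, the plan implies in-session marker placement by someone who knows the condition, and the reason given in 3.9 does not justify leaving the reading unmasked. The primary measurement is therefore open to reader bias of unknown size and direction. The rates tabulated above show only how sensitive so small a study could be; they depend on the assumed test, zero true movement and the assumed bias.

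A reader might infer that the pilot is invalid or its endpoint worthless. The documents do not support that: this is a small exploratory study, and the issue restricts how firmly its result can be offered as objective evidence. It merits a change because partial protection costs little and leaves the sample size untouched.

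**What to change.** 1. **Amend 4.4 on image capture.** For each condition and each repeat, save a rest frame and a contraction frame, or a short clip spanning both, without markers or condition labels. Hold the probe in the same position for the pair, and save before any probe manipulation to identify muscles.
2. **Code the files.** An existing site or sponsor staff member who does not do the measuring assigns random codes.
3. **Read masked.** The existing operator locates the bladder base in the coded frames in random order, after all sessions where possible to limit recall. This reading is the primary value and the live reading is supportive.
4. **Reword 3.9.** State that marker placement is masked to condition, but that acquisition is not, nor the choice of maximal frame if only stills are kept. Report this as a limitation.

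**Cost.** No extra reader, visit or scanning session is needed. Paired frames mean 3 conditions × 2 repeats × 2 frames = 12 per woman, or 96 for 8 women and 144 for 12, against the 56-84 images already required. That is a few hours of re-measurement (a judgement, not a figure in the documents) plus file handling. The protection is partial; clips cover more than stills because the maximal frame can then also be chosen under masking.

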#### 8.4.1 Primary Outcome

- Movement of pelvic floor with electrical stimulation

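### The stimulation-only condition, which supplies the primary outcome, carries no instruction to stay relaxed, so any voluntary contraction would be counted as movement caused by SES

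*Combined protocol and SAP*

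**What the plan says.** The primary endpoint in section 1.1 is "Displacement of bladder base during contraction", and section 8.4.1 gives the primary outcome as "Movement of pelvic floor with electrical stimulation". Section 2.2 explains the motive: users had already confirmed contractions themselves, and "a more objective proof that the pelvic floor is actually contracting was requested".

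Section 4.4 lists three required conditions and one optional one.

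- Condition 1 is a Kegel with a standardised cue: "Instructions should be the same to all: to draw in and lift the PFM".
- Condition 2 is stimulation alone: "with the generator on, slowly incrementing, counting the clicks and making note of when they first feel a contraction", continuing to the highest comfortable intensity. It covers the generator, the click count and the sensation to be noted. It says nothing about what the woman should do with her own muscles.
- Condition 3 is stimulation at that intensity while "doing a PFM Kegel contraction combined".
- Condition 4 (optional) is a second waveform, also without an instruction to the subject.

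Rest enters only as the reference for the marker: "A marker should be placed at the bladder base on the junction of the hyper- and hypo-echoic areas in the region at rest". A second marker records the largest displacement from that position. The set is then repeated, and subjects do not see the image. Section 3.9 treats randomisation and blinding as not applicable. Section 5.3.2 gives a cycle of 6 s on and 6 s off, with no off-phase measurement.

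**The concern.** Displacement shows that the bladder base moved, not what moved it. The recorded measure does not separate a lift evoked by the device from one the woman makes herself. Because the largest displacement is marked, a brief voluntary lift within the take could set the recorded value.

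The authors recognised that wording to the subject matters, since they standardised it for the Kegel. They did not do so for the condition on which the primary outcome rests. In that condition the woman is asked to attend to a contraction while she herself raises the intensity (sections 4.4 and 6.1).

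Two results are exposed. One is the primary displacement, which is meant to be more objective than the user's own report. The other is the comparison of stimulation, Kegel and both in section 8.4.2.

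**Working it through.** **Is there an instruction or check elsewhere?** The protocol text contains no relaxation instruction, return-to-rest check before stimulation, sham or zero-output take, off-phase reading, or measure of voluntary effort. The one stated figure bearing on the sequence is the minimum image count in section 4.4. It reproduces: 1 baseline + 2 Kegel + 2 generator + 2 combined = 7. A single resting image therefore serves both rounds.

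**Effect on the measurements.** Let S be the true evoked lift, K the woman's Kegel lift, and f the fraction of K she adds during condition 2. The documents give no value for any of these. Assume that lifts add and that condition 3 gives S + K.

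- Condition 2 reads S + fK, so the primary displacement is inflated by fK.
- Both minus stimulation reads (S + K) − (S + fK) = K(1 − f), against a true K.
- The stimulation-versus-Kegel gap is truly |S − K| and is read as |S + fK − K|. If S ≤ K(1 − f), the read gap is smaller by fK. If S lies between K(1 − f) and K, the read gap is S − K + fK, which is below K − S only when 2S < 2K − fK, that is S < K(1 − f/2). Above that value the gap widens. At S = K, for example, it goes from 0 to fK.

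| f (assumed) | Inflation of primary reading | Both minus stimulation | Gap narrows only if S is below |
|---|---|---|---|
| 0.25 | 0.25K | 0.75K | 0.875K |
| 0.50 | 0.50K | 0.50K | 0.75K |

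In the extreme case S = 0, the device would appear to produce 25% to 50% of a Kegel.

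**Effect in a sample of this size.** Section 3.3 gives a goal of 8 subjects, a minimum of 5 and a maximum of 12. Suppose that stimulation moves nothing and that each woman independently contracts in condition 2 with probability q (assumed). The chance that at least one shows lift is 1 − (1 − q)^n.

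| q | n = 5 | n = 8 | n = 12 |
|---|---|---|---|
| 0.10 | 41% | 57% | 72% |
| 0.25 | 76% | 90% | 97% |
| 0.50 | 97% | 99.6% | >99.9% |

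At n = 8, the binomial chance that at least half (4 or more) show lift is 0.5%, 11% and 64% for the same three values of q. Isolated false lifts would be easy to obtain. A majority pattern would need frequent co-contraction.

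**The case against.** The strongest reply is that condition 2 is already defined as non-voluntary. Section 4.4 sets it against a combined condition, counts the generator images separately from the combined ones, and measures from rest. Section 8.4.2 likewise names three distinct states. This stands as a statement of intent to staff, but none of it is said to the woman. Hiding the image removes visual feedback, not effort.

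Several stronger readings are tempting, and the documents do not support them.

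- A reader might infer that women go into stimulation directly from a coached Kegel. The numbered order suggests it, but no interval or mandatory order is stated, a stimulation test precedes the first study Kegel, and the intensity rises slowly from 0. The missing instruction matters whatever the order.
- A reader might infer that squeezing along or guarding is the usual response. No section says so, and intensity that the subject controls and keeps comfortable could reduce guarding.
- A reader might assume that bracing looks the same as an evoked lift. Section 4.4 gives no direction for the displacement and does not describe how bracing or breath-holding appears. The algebra above covers Kegel-like effort only.
- A reader might conclude that the stimulation-versus-Kegel comparison is biased towards equivalence. That holds only for S below K(1 − f/2).

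The cited ultrasound methods, the CRF and the separate appendices were not available. An instruction there can be neither assumed nor ruled out, but section 4.4 sets out the measurement procedure and is where it belongs. Finally, this is a small single-arm pilot with no stated hypothesis test. That limits the consequence, although attributing movement to the device remains its purpose.

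**Conclusion.** The concern holds in limited form. As written, the plan cannot separate voluntary from evoked movement in the condition that carries its primary outcome, and it would not detect the difference. The documents establish that this is possible. They do not establish that it occurs, or how much.

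Under the additive model with f assumed at 0.25 to 0.5, the primary reading is inflated by 0.25K to 0.5K and the gain of both over stimulation falls to between 0.75K and 0.5K. These sizes rest entirely on the assumed f and on additivity. No general direction can be claimed for the stimulation-versus-Kegel comparison. The change is worth making before the first subject because it reduces bias in the primary measure at very little cost.

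**What to change.** Add to condition 2, and to optional condition 4, one fixed script read the same way to every subject: stay relaxed, breathe normally, and do not squeeze, lift or hold against the stimulation.

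After each such take, record on the CRF whether the subject reports having contracted and whether the operator saw bracing or breath-holding. Keep all takes in the primary displacement, list the flagged ones, and give a sensitivity summary without them. Write this rule into the statistical analysis plan that section 9.4.3 promises before any analysis.

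Flagged takes should not be removed from the primary result. Doing so would make the endpoint depend partly on the subject's own report, which the study was meant to improve on, and could drop whole subjects from a sample of 5 to 12. Nor should a repeat be compulsory. It means another full ramp, and section 4.4 itself notes that the skin may become numb and the intensity rise.

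The cost is one scripted sentence, one CRF item and one extra summary, with no change to any stimulation setting. The script and flag reduce and document the risk. They do not prove objectively that a subject stayed relaxed.

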### 5.3.2 Generator Settings

- Freq: 2000Hz modulated at 50 Hz (sinewave), *Waveform B (same but square wave)*
- Timing: 6 sec on, 6s off
- Intensity: Current (mA) should be at max tolerable level, ideally to be increased, must record.

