#### 8.4.2 Secondary Outcomes

- Comparison of movement with electrical stimulation, Kegels, and both
- Indication of which muscle groups are activating

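### Section 4.4 scores maximal displacement over an undefined and possibly unequal window: a ramp of bursts for stimulation alone, one contraction for Kegel and for Kegel plus stimulation

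*Combined protocol and SAP*

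**What the plan says.** In section 4.4 one instruction governs all conditions: "A marker should be placed, marking the maximal displacement of the bladder base from resting position". The list under it then describes what happens while that marker is set.

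- **Kegel:** "while doing a PFM Kegel contraction", in the singular.
- **Stimulation alone:** "with the generator on, slowly incrementing, counting the clicks and making note of when they first feel a contraction", continuing "until a maximum comfortable intensity level".
- **Kegel plus stimulation:** one voluntary contraction made at the top comfortable level.
- **Second waveform (optional):** at the top comfortable level.

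The sequence is then repeated, possibly at a higher intensity. "There should be a minimum of 7 ultrasound images", split as one baseline and two for each of the three main conditions. Section 5.3.2 gives the burst cycle: "Timing: 6 sec on, 6s off".

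The readings feed the first secondary outcome in 8.4.2, "Comparison of movement with electrical stimulation, Kegels, and both". The stimulation reading is also the primary outcome (8.4.1). No rule says how the two passes are combined. Sections 9.2 and 9.4.3 leave the analysis to a statistical analysis plan still to be written.

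**The concern.** A maximum grows with the number of noisy contractions it is chosen from, even when the true displacement is the same. Only the stimulation condition is worded as a ramp ending at the top level; the other stimulated conditions are read at that level. A separate trial of the device, with the intensity raised slowly, already comes before imaging, so the ramp within the stimulation condition is not plainly mere set-up.

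On the literal reading, call the excess from choosing the best burst b. Then:

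- observed stimulation minus Kegel = true difference + b
- observed (Kegel plus stimulation) minus stimulation = true gain − b

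Identical instructions and practice in every condition would not remove b, because it comes from the scoring window. The study has no comparator arm and plans 8 women (5 to 12), so this within-woman contrast is the only comparison it offers. If only selected maxima are stored, an unequal window cannot be undone in the analysis.

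**Working it through.** **Figures in the plan.** The image count reproduces: 1 + 2 + 2 + 2 = 7. It fixes how many images are stored, not how many contractions each stored maximum is chosen from. The documents give no SD, effect size, alpha or test, so there is no power figure to reproduce.

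**Bursts in a ramp.** One cycle is 6 + 6 = 12 s, so 60 / 12 = 5 bursts a minute. The automatic shut-off at 20 minutes (section 6.1, other safety considerations) caps a ramp at 20 × 5 = 100 bursts. The length of the ramp is not stated. I assume K = 5, 10 or 20 bursts, which is 1, 2 or 4 minutes.

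**Model (assumed).** Let s be the contraction-to-contraction SD. Burst j has true displacement μ_j, rising in equal steps from 0 at the first burst to D at the last. The comparator is one contraction with true displacement D, so the true difference is zero. In units of s, the excess is

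b = E[max_j(μ_j + Z_j)] − D, with Z_j independent standard normal.

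| K bursts | D = 3 SD | D = 5 SD | D = 10 SD |
|---|---|---|---|
| 5 | 0.33 | 0.16 | 0.02 |
| 10 | 0.67 | 0.45 | 0.19 |
| 20 | 1.01 | 0.78 | 0.47 |

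Starting the ramp one step above zero (μ_j = D·j/K) moves the corner values only slightly: 0.05 for K = 5, D = 10, and 1.03 for K = 20, D = 3.

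**End-of-ramp reading.** If one burst at the top level is scored, K = 1 and b = 0.

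**More than one contraction watched in the comparators.** The expected maximum of m contractions with the same mean exceeds that mean by 0.56 SD (m = 2) or 0.85 SD (m = 3). Subtracting this from the K = 10 row:

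- m = 2: 0.67 − 0.56 = +0.11 (D = 3); 0.45 − 0.56 = −0.11 (D = 5)
- m = 3: 0.67 − 0.85 = −0.18 (D = 3); 0.45 − 0.85 = −0.40 (D = 5)

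The sign depends on habits that the protocol does not fix.

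**What it could do to a test (illustration only).** I simulated 8 women, two passes averaged, equal true means, one comparator contraction per pass, no variation between women in the true difference, and a two-sided 5% paired t-test. The test declares a difference in about 5% of trials for K = 5, D = 10, in about 84% for K = 20, D = 3, and in the nominal 5% for K = 1. If women also differ in their true stimulation–Kegel difference, the inflated rates are lower.

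**The case against.** The strongest reply is that the text does not say the marker is the best of the ramp. The stimulation instruction ends at the top comfortable level, the later conditions are read at that level, and the protocol speaks of three images being recorded per pass. An operator could well ramp up, arrive, and capture the peak of a single burst. Maximal displacement may simply mean the peak of one contraction, as it must for a Kegel. This reading is fair, and with one burst it carries no bias.

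A reader might go further and infer that the comparison favours stimulation by construction. The documents do not support that. Besides the end-of-ramp reading, the singular wording for a Kegel is ordinary prose rather than a stated limit of one attempt, and several bursts could equally be watched in the combined condition.

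A reader might also treat every burst in the ramp as an equal candidate. That gives an excess of 1.16 SD for five bursts and, in the same kind of simulation, a paired test rejecting in about 92% of trials. A ramp need not behave that way: if displacement rises with intensity, early bursts seldom supply the maximum, and five bursts give 0.02 to 0.33 SD.

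Nor does the wording on a minimum number of images direct extra images to the generator condition; the stated minimum is equal across conditions. Equal image counts still leave open how many contractions each image was selected from, so that part of the reply does not dispose of the point.

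Finally, this is a secondary comparison in a small pilot, the documents name no test, and an analysis plan is to follow. That lowers the stakes. A later plan can say how to combine readings, but it cannot recover contractions that were not recorded.

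**Conclusion.** The point holds as an undefined and possibly unequal measurement window. On the literal wording, stimulation alone has more contractions to choose from. This can raise it against Kegel and shrink the apparent gain from adding a Kegel; it does not mean that the combined condition must come out lower. Under the assumed linear ramps, with one comparator contraction, the excess is about 0.02 to 1.0 SD. It is zero if one end-of-ramp burst is scored, and it can reverse if two or three contractions are watched in the comparators. The number of bursts, s and the dose response are all assumptions, so neither the size nor the direction in this trial can be predicted. Two sonographers following the same text could produce values that are not comparable.

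**What to change.** In section 4.4:

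1. State that the ramp serves only to find the level and is not scored.
2. With the level then held, score the same prespecified number of contractions per pass in every condition: on-phases for stimulation, Kegels for Kegel, and Kegels made within an on-phase for the combination.
3. Name one summary, maximum or mean, and apply it alike to each condition and to the two passes. Either is acceptable once the counts are equal, so changing from a maximum to a mean is optional.
4. Replace the minimum image count with an equal fixed number of scored images per condition. Extra images may be kept but are not scored.

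This removes the imbalance under either reading and leaves the generator settings as they are. It costs one paragraph in 4.4, a line on the case report form and a minute or two more imaging per woman. The reported stimulation displacement may be somewhat smaller.

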### 4.3 Pre-test

Subjects will be instructed to follow a standardized bladder-filling protocol, consisting of voiding, drinking 500 ml of water and waiting 45-60min (ideally 60 min before US pictures taken, but set up may start earlier).

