While the generator is on the ultrasound probe can be manipulated to see if there is any evidence or indication which muscles are being contracted. We want to understand which muscles in terms of depth (pelvic diaphragm with levator ani, or perineal pouch with sphincter urethrovaginalis, or more shallow perineal membrane) which may also help determine if localized around urethra or entire pelvic floor, and if there is a difference between Kegels and electrical stimulation.

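### Section 4.4 requires one rest image for six contraction images and does not keep the probe search separate, so later displacements may be read from an outdated rest position

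*Combined protocol and SAP*

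**What the plan says.** The key endpoint in section 1.1 is displacement of the bladder base. Section 4.4 defines it with two markers. For the first, "A marker should be placed at the bladder base on the junction of the hyper- and hypo-echoic areas in the region at rest". For the second, "A marker should be placed, marking the maximal displacement of the bladder base from resting position", in three required conditions: Kegel, generator, and both together. The round is then done again: "After the three images and max displacement recorded, the test should be repeated and potentially the intensity increased to a new maximum level". The required set is "There should be a minimum of 7 ultrasound images (1 baseline, 2 with Kegels, 2 with generator, 2 with Kegels and generator". No sentence asks for rest to be imaged or marked again before a condition or before the second round.

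Three other statements bear on whether the rest position stays put:

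- Section 4.3 has a timed bladder-filling step, "consisting of voiding, drinking 500 ml of water and waiting 45-60min (ideally 60 min before US pictures taken, but set up may start earlier". It sets no bladder-volume check and no limit on how long imaging may last.
- The generator step in section 4.4 is gradual: "with the generator on, slowly incrementing, counting the clicks and making note of when they first feel a contraction, until a maximum comfortable intensity level". Its duration is not stated.
- The last paragraph of section 4.4 says "While the generator is on the ultrasound probe can be manipulated" to look for the muscles involved. It does not place this search after the displacement images, and it does not ask for the probe to be returned or rest to be imaged again.

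Section 5.3.2 gives the stimulation cycle as 6 s on and 6 s off. Section 3.3 describes a single-arm pilot without a comparator. Sections 9.2 and 9.4.3 leave the analysis plan to be written later.

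**The concern.** Displacement is read between two markers in an image from a hand-held probe. It equals movement of the bladder base only if the rest marker still marks the same anatomy when the contraction marker is placed. The plan repeats every contraction image but not the rest image. It also allows two things that could move the reference in between: tilting or sliding the probe, and further filling after the water load.

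The study exists to give more objective evidence of contraction than the subject's own report (section 2.2). With no comparator, nothing else in the design would show that part of a recorded displacement came from a shifted reference. The outcomes exposed are movement with stimulation (section 8.4.1) and the comparison of stimulation, Kegel and both (section 8.4.2). A later analysis plan cannot recover rest frames that were never captured.

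**Working it through.** **Image count.** Section 4.4: 1 + 2 + 2 + 2 = 7, which reproduces the stated minimum. A rest frame for each contraction would give 6 + 6 = 12. One rest frame per round would give 2 + 6 = 8.

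**Probe tilt.** The documents give neither depth nor tilt. Assume the bladder base lies 60–100 mm from the probe face and the probe tilts 1–2 degrees in plane.

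- Across the beam, shift = depth × tan(tilt):
  - 1 degree: 60 × tan 1° = 1.05 mm; 100 × tan 1° = 1.75 mm
  - 2 degrees: 60 × tan 2° = 2.10 mm; 100 × tan 2° = 3.49 mm
- Along the beam, for a target on the axis, shift = depth × (1 − cos(tilt)): from 60 × (1 − cos 1°) = 0.01 mm to 100 × (1 − cos 2°) = 0.06 mm.

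Off-axis targets fall between these. The plan does not state the direction in which displacement is measured, so 1.0–3.5 mm is an upper case.

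**Steady drift.** No drift rate is given. Assume the rest position drifts b mm per image step and the listed order is kept, with one rest image at step 0. Kegel is then at steps 1 and 4, generator at 2 and 5, and combined at 3 and 6. Mean false displacement:

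| Condition | One rest image | One per round | One before each contraction |
|---|---|---|---|
| Kegel | (1 + 4)/2 = 2.5b | 1b | close to 0 |
| Generator | (2 + 5)/2 = 3.5b | 2b | close to 0 |
| Combined | (3 + 6)/2 = 4.5b | 3b | close to 0 |

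For b = 0.1, 0.25, 0.5 and 1.0 mm, the generator figure with one rest image is 0.35, 0.875, 1.75 and 3.5 mm. Generator minus Kegel is off by b. One rest image per round does not remove that: 2b − 1b = b.

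**Effect on a test, for illustration only.** The plan names no test. Suppose a two-sided 5% one-sample t-test, zero true movement, and a bias in the same direction in all subjects equal to 0.5 of the between-subject SD. The test would reject in 14.1% of trials at n = 5, 23.2% at n = 8 and 35.3% at n = 12. More subjects do not cure a shared offset. If the shift varied in sign between subjects, it would add noise instead.

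**Reading error without drift.** Take equal, independent reading variance of 1 for rest and contraction frames. For a two-reading mean displacement, a shared rest image gives 1 + 0.5 = 1.5 and paired rest frames give 0.5 + 0.5 = 1.0. For generator minus Kegel, a shared rest reading cancels, giving 0.5 + 0.5 = 1.0, whereas paired frames give 1.0 + 1.0 = 2.0. Pairing therefore helps the primary outcome and costs some precision in the contrast, in exchange for removing drift and probe shift from both.

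**The case against.** The best defence is that section 4.4 can be read as rest-to-peak within each manoeuvre. The displacement instruction introduces the numbered conditions, and seven images is a floor that does not forbid more rest frames. Section 4.1 also says that published methods will be used, and sections 4.3 and 4.4 cite them; whether they re-mark rest cannot be checked here. The probe search is optional, serves the secondary objective, and is described after the imaging sequence. If it is done last, the probe-shift part is zero. These points stand. They show that a careful site may avoid the problem, but not that the protocol requires it to.

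Four stronger readings are tempting, and the documents do not support them:

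- *Later images do carry an offset.* Continued filling is inferred from the timed water load. Its size and direction are unknown, and nothing shows that the probe is moved between rest and contraction frames.
- *Probe shift falls only on the stimulation conditions.* The search is described with the generator on, so it spares the first Kegel image. A search during round one would also reach the second Kegel image.
- *The problem would persist whatever off-period reading is taken.* A reading in the off phase next to the on phase is a local rest, and on minus off cancels a common offset. The plan does not require such a reading.
- *The error is 1–3.5 mm.* That is the across-beam case under assumed depth and tilt.

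**Conclusion.** The point holds as a gap in the acquisition rule. The plan requires one rest image for six contraction images, does not require rest to be re-marked, and does not keep probe movement apart from the displacement images. A compliant site could therefore record probe shift or filling as part of the primary outcome and of the stimulation-versus-Kegel comparison.

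The documents give no drift rate, depth, tilt, measurement error or expected displacement, so neither the size of the error nor its share of true movement can be stated. It could add to movement or hide it. For a pilot of 8 subjects (5 to 12) with no stated test or success threshold, this is a should-fix improvement and not a defect that invalidates the study.

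**What to change.** In section 4.4:

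1. Require a rest frame immediately before each contraction, with the subject relaxed and the probe not moved between the two frames. For Kegel alone, take it with the generator off. For the generator and combined conditions, take it in the 6 s off phase of the existing cycle (section 5.3.2). This matters because section 6.1 says intensity starts from 0, and a full switch-off could mean ramping up again.
2. Compute each displacement from its own rest frame.
3. Raise the minimum from 7 to 12 images (6 rest + 6 contraction). If the optional Waveform B images are taken, pair them in the same way.
4. Do the probe search only after all displacement images are captured.

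The cost is 12 − 7 = 5 extra stills per subject, one or two sentences in section 4.4 and a line on the case report form, with the probe already in place. The statistical cost is the extra reading error in the between-condition contrast shown above. The off-phase frame also assumes that the muscle has relaxed by the time it is taken. One rest image per round (8 in all) would be lighter, but it would leave drift within each round.
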